Appendix E. Data Safety Monitoring Plan (DSMP)

 National Institute on Alcohol Abuse and Alcoholism	Version: DSMP V1
	Effective Date: 01JUN17
NIAAA Data and Safety Monitoring Plan (DSMP)	
PI Name: [name]	Grant Number: 1R01AA025043-01A1
Approval Date: LEAVE BLANK	LEAVE BLANK

Instructions: At a minimum, the DSMP must include the following critical elements as outlined on the [NIAAA website](#) and provided below. Please provide an answer addressing each critical element. If one of the elements does not apply to your study, please respond N/A.

1. A description of the entity(ies) responsible for monitoring the trial (e.g., an independent monitoring group or person, DSMB, etc.) and procedures for monitoring subject safety.

[name], Contact PI, will have primary responsibility for monitoring the trial assisted by the other PIs who will meet as a team biweekly, as well as the DSMB that convenes twice per year.

The project coordinator will download and review all data on a monthly basis. Our data management plan contains periodic data quality checks, early generation of analysis variables, and interim data summaries to provide a check on completeness of study data. The full analysis plan will be executed on collected data at the end of the RCT to ensure that we have correct variables and fix errors so final analyses can be completed quickly.

The screening survey will be completed anonymously, and screening data are unlinked to contact information obtained in the scheduler, so that we will not know the identities of students who complete the screener. During the RCT, face-to-face contact with participants is limited to the baseline/intervention session; research staff will be trained to identify adverse events (defined below) and report the to the site-specific contact. Similarly, any safety concerns raised by participants through study-related electronic/phone communications will be reported by research staff to the site-contacts, who will be prepared to provide referrals to their respective campus counseling centers. Finally, electronic surveys completed by participants will not be monitored at an individual basis, because of assurances that responses to questions will not be associated with names, but each will end with a list of counseling centers and alcohol and drug services, as well as the number for a 24-hour crisis hotline.

A. DSM BOARD PLAN

Because this multisite prevention study involves a relatively low risk protocol and a non-clinical participant pool, we propose to rely on the standing DSMB that meets monthly at the Center for Alcohol and Addiction Studies. The members will consist of **3 faculty members** with experience in conducting clinical trials, who have no conflict or role with the current study. This project will be reviewed **every 6 months**, and at these meetings the DSMB will evaluate the progress of the trial, review recruitment and retention rates, and examine any factors that may affect outcome. The DSMB reviews compliance with eligibility criteria and adherence to protocol safety rules. The DSMB will also review the rates of adverse events and serious adverse events to determine any changes in participant risk. DSMB members will be local to the prime site, permitting rapid communication with both research teams and IRB and the ability to convene quickly on issues related to participant safety or other problems, if necessary.

B. CONFLICT OF INTEREST

Before being asked to serve on the DSMB, the PI will ensure that members do not have a conflict of interest. The PI will also check that members are not in conflict prior to all Board meetings in case something with respect to their status has changed.

C. PROTECTION OF CONFIDENTIALITY

Participants will only be identified by number during review of study progress by the DSMB. We are not collecting data requiring that confidentiality be breached.

D. COMMUNICATION PLAN

A report will be submitted by the investigators **to the DSMB** twice a year, containing the following categories:

- i. Brief description of the trial
- ii. Baseline sociodemographic characteristics
- iii. Recruitment rates
- iv. Retention and disposition of study participants
- v. Q.A. and data monitoring issues
- vi. Summary of AEs and SAEs and actions taken
- vi. Summary of changes to participant risk and to protocol

The report submitted **after each DSMB** meeting to the IRB and NIAAA PO will include:

- i. Brief description of the trial
- ii. Summary of discussion
- iii. DSMB recommendations/action items
- iv. signature of DSMB members

2. Name of the responsible party (e.g., Principal Investigator, Study Physician if different than PI) who will distinguish a serious adverse event (SAE) from a non-serious adverse event (AE) and provide attributions (causality and severity). Provide a detailed accounting of how SAEs, AEs, and unanticipated problems will be managed consistent with local IRB guidelines (e.g. reporting requirements).

Each site has a designee who will take responsibility for distinguishing serious adverse events from non-serious adverse events: [name] (licensed clinical psychologist) for the Brown sample and [name] for the Houston sample. [name] (who also holds a masters in clinical counseling) will serve as back-up for both sites, due to his familiarity with both. In the proposed study we will use the FDA definition of adverse events (AE) and serious adverse events (SAE). An adverse event is any untoward (unexpected and undesirable) physical or psychological occurrence, serious and non-serious, in a participant that may have a causal relationship with study participation.

Symptoms or conditions present at or before the assessment that manifest themselves with the same intensity or frequency after study participation will not be recorded as adverse events. Although deemed highly unlikely, research staff will be trained to observe and report any unanticipated or adverse reactions reported by participants. The baseline session represents the only instance of face to face contact with participants. All other assessments are completed remotely online. Any concerns will be immediately reported to the investigators, who will review the information and classify the relationship of the study protocol to the event as:

- *Not related*: The event is clearly related to the participant's clinical state, not with the study protocol
- *Remote*: Event was most likely related to the participant's clinical state, not with the study protocol
- *Possible*: Event follows a reasonable temporal sequence associated with participating in the study but is possibly related to the participant's clinical state.
- *Probable*: Event follows a reasonable temporal sequence associated with participating in the study and cannot be explained by the participant's clinical state.

The scale below will be used to estimate the grade of severity of the adverse event:

- *Grade 1 Mild*: Transient or mild discomfort, no limitation of activity, no or minimal intervention/therapy required.
- *Grade 2 Moderate*: Mild to moderate limitation in activity; some assistance may be needed; no or minimal intervention/therapy required.
- *Grade 3 Severe*: Marked limitation in activity; some assistance usually required; intervention/therapy required; hospitalization possible.
- *Grade 4 Life –threatening*: Extreme limitation in activity; significant assistance required; significant intervention/therapy required; hospitalization probable (SAE).

3. A description of the follow-up plans for SAE and unresolved unanticipated problems.

During the intervention phase of the study the research staff will convene separately at both sites on a weekly basis to discuss study progress and potential problems. Informed consent forms will list the contact phone numbers for site PIs so that any potential adverse events or complaints can be reported by the students directly to the site PI or designee. In addition, the consent form will include the contact phone numbers for appropriate Brown University IRB personnel so that participants can directly report any complaints or potential adverse events.

4. Risks associated with study participation.

In our previous research in similar research projects at similar venues, no adverse events have occurred; therefore, in the proposed project, we anticipate the likelihood of an adverse event to be minimal.

5. Confirmation that SAEs and unanticipated events which are considered “at least possibly related” during the treatment and follow-up phases will be reported to the local IRB and to NIAAA within 48 hours of knowledge of the SAE and all other SAEs and unanticipated events must be reported within the time period mandated by the local IRB.

Yes. In the case of a serious event, a written report will be provided to the Brown University IRB (as Brown will serve as the IRB of record for both sites), and to the NIAAA project officer within 48 hours of the initial reporting of the event. Any actions determined by the Brown University IRB as a result of any adverse event also will be reported to NIH

6. A statement confirming that the Annual Report will include the following: a summary of all AEs, confirmation of adherence to the DSMP, a summary of any data and safety monitoring issues since prior reporting period, a description of the changes in the research protocol or DSMP and all new and continuing IRB approvals.

The annual report to NIAAA will include all AEs, confirmation of adherence to the DSMP, a summary of any data and safety monitoring issues since prior reporting period, a description of the changes in the research protocol or DSMP and all new and continuing IRB approvals.

7. Study inclusion and exclusion criteria

Inclusion criteria for RCT:

- (1) Age 18-26
- (1) Male or female student at Brown University or University of Houston
- (2) Past month heavy episodic drinking (for men, >5 drinks in one day, for women >4 drinks in one day)
- (3) At least two self-reported negative consequences from drinking in the past month

Exclusion criteria for RCT:

- (1) Students that have requested that the university not share information about them will not be contacted during recruitment
- (2) status as a senior graduating in the next 6 months

8. A statement confirming that trained clinical staff will be present or on call when study procedures take place, based on level of risk and consistent with approved protocol, policies and guidance from the local IRB and/or other regulatory and monitoring entities. Examples include (but are not limited to) the administration of alcohol, other drugs and/or medications; invasive or other study procedures or testing; etc. The types of trained personnel (e.g.: nurse, nurse practitioner, physician assistant, physician, etc.) should be stated.

The current study involves no invasive procedures requiring trained clinical staff, as participants will be engaged in completing survey questionnaires, engaging in self-directed writing tasks and discussing them with a research assistant. Nonetheless, we will designate a responsible person at each site who can be on call in the event of an adverse event. At the Center for Alcohol and Addiction Studies at Brown, [name], is a licensed clinical psychologist has relevant experiences in clinical research, and staff training and supervision. At Houston, the designee will be [name], a research staff member.

9. For studies in which alcohol is administered, provide assurance that NIAAA guidelines for the administration of alcohol will be followed. These guidelines can be found here: [Alcohol Administration Human Laboratory Studies](#).

N/A

10. Describe the plan for referral to treatment during follow-up phases for any research participant who requires additional intervention due to significantly increased alcohol consumption or serious psychiatric/medical symptoms.

The follow-up phases of this research involve electronic communications with participants and online surveys. Data will not be monitored at the individual level for changes in clinical status. However, at the end of each online survey, participants will be provided with the phone number for a 24-hour crisis hotline, as well as a list of counseling centers and alcohol and drug resources, including ones both inside and outside of the Universities.

11. Describe procedures for data quality assurance and protecting confidentiality of participant data (e.g., [Certificate of Confidentiality](#)).

We will follow data collection, storage, and management procedures that protect participant confidentiality. All data will be identified only by a unique subject identification number, which will be stored separately from identifying information. In addition, contact information will be collected and stored separately from survey responses, and will only be accessible to trained research staff that need to use it. Assessment data are stored on a secure server with a firewall to protect the data and to prevent unauthorized access.

Databases on the server are password protected and will be accessed only by research staff who have met the Brown University or University of Houston requirement for training in Human Subjects Protections. We will not share any specific information about participants with any other departments or offices at Brown University or the University of Houston.

12. Provide a statement indicating certification of IRB approval(s) of the study protocol will be provided to NIAAA prior to screening study participants. IRB approvals should be submitted (preferably electronically) to the NIAAA Grants Management Officer (GMO) before initiating a proposed clinical trial. For multi-site studies, the Data Coordinating Center (DCC) and associated study sites must submit certification of IRB approval as well as assurance that IRB approvals have been obtained for all study sites, are on file at the clinical site and DCC, and are available to the NIAAA upon request.

We confirm that an IRB application will be submitted through Brown University. Brown University will serve as the IRB of record and an IAA has been set up between Brown University and the University of Houston indicating that Brown University is the IRB of record. No recruitment or data collection will take place prior to full IRB approval.

13. Provide the analysis plan including the power calculation(s). There should be discussion of any planned interim and/or futility analyses, including adjustments for allocating “alpha” on “multiple looks” at the data.

Sample size and power calculations. Power analyses focus on estimating a sample size large enough to detect “true” effects, thereby avoiding Type II errors. Sample size estimates were obtained for intervention contrasts. Necessary sample sizes were assessed via sample size and power equations for multi-level models using the Optimal Design software program.

Based on previous findings using CAA and PNF approaches, we anticipate intervention effects relative to the neutral control condition to be in the small to medium range but at least comparable to effects which have been reported for personalized normative feedback, which are typically in the .28 range (e.g., Dotson et al., 2015). Based on the proposed sample size of 600, given four assessment points, we anticipate the ability to detect effects of intervention contrasts and moderation effects across the small to medium range.

Considering maximum anticipated attrition rates of 15% (N=510) we will have .70, .80, and .90 power to detect effects sizes of delta = .24, .27, and .32, respectively.

14. Provide the study stopping rules part of the study protocol. Generally, stopping rules reflect one of the following conditions: 1) there is clear evidence of harm; 2) there is no likelihood of demonstrating treatment benefit (futility); 3) there is overwhelming evidence of the benefit of treatment.

There are no study stopping rules associated with the current protocol. Based on prior research, there is no reason to believe that the interventions used in this study could cause harm. Therefore, we do not plan interim analyses prior to achieving our full sample. We anticipate that the full sample will be needed to have sufficient power to detect significant group differences.

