11. RISK/BENEFIT ASSESSMENT

11.1. Possible Risks. The level of risk that our volunteer participants will be exposed to by completing online surveys of their drinking practices and related cognitions, or by engaging in writing or computer feedback activities about promoting safer drinking practices on campus is minimal. The main risks of participation include (a) a breach of confidentiality or (b) discomfort or distress answering questions about drinking behavior and/or consequences.

Confidentiality could be breached by research staff or if data stored electronically were accessed by an unauthorized source. The seriousness of the consequences of a breach of confidentiality would depend on the nature of the information revealed and to whom the information was revealed. Some participants will be under the legal drinking age of 21, and will be reporting past episodes of underage drinking. However, this is a relatively small risk because, as a general rule, reports of past drinking carry minimal legal liability because of the difficulty in proving the behavior after the fact. Given the numerous steps we take to protect participant confidentiality (as described below), we think the risk of a breach of confidentiality is low.

Participants may feel uncomfortable or distressed answering questions about their drinking behavior on surveys. Participants will have been informed of the types of questions they will be asked to answer, and they likely would not choose to participate if these types of questions made them feel uncomfortable. Participants have the option of refusing to answer the questions or withdrawing from the

study if they think the questions are too personal. In our previous research using similar survey questions with thousands of college students, none of the participants reported being significantly distressed by the questions. At each assessment point, participants will have the option to download a Resource Sheet with contact information for substance abuse and mental health services (see Appendix C, Mental Health Safety Plan).

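### The adverse-event definition in DSMP item 2 builds in unexpectedness and possible study causation, which conflicts with the plan's own attribution, severity and reporting rules and risks undercounting AEs

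*Combined protocol and SAP*

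**What the plan says.** Appendix E, DSMP item 2, says that the FDA definitions of AE and SAE will be used; their text is not reproduced. It then gives its own wording: "An adverse event is any untoward (unexpected and undesirable) physical or psychological occurrence", serious or non-serious, "in a participant that may have a causal relationship with study participation". Conditions already present that continue at the same intensity or frequency are not recorded as AEs.

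The same item has staff report unanticipated or adverse reactions and has any concerns sent at once to the investigators. They assign one of four relationship classes: *Not related*, *Remote*, *Possible* or *Probable*. The first is worded: "The event is clearly related to the participant's clinical state, not with the study protocol". The severity scale starts at Grade 1, which covers transient or mild discomfort. Only Grade 4 carries an SAE tag. Grade 3 reads: "Marked limitation in activity; some assistance usually required; intervention/therapy required; hospitalization possible".

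DSMP item 5 asks the sponsor to confirm 48-hour reporting of SAEs that are at least possibly related, and that "all other SAEs and unanticipated events must be reported within the time period mandated by the local IRB". The answer is yes, followed by a 48-hour commitment for a serious event.

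Section 11.1 states: "The main risks of participation include (a) a breach of confidentiality or (b) discomfort or distress answering questions about drinking behavior and/or consequences".

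**The concern.** Whether an event happened, whether it was foreseen and whether the study caused it are three separate questions. Item 2 makes the second and third part of the first. An event judged expected, or clearly not study-related, is then not an AE at all, and the later attribution step has nothing to work on.

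This matters because the plan's safety outputs are stated in terms of AEs. The DSMB reviews AE and SAE rates to detect changes in participant risk (item 1.A). The twice-yearly report to it contains a summary of AEs and SAEs (item 1.D). The annual report to the funder lists all AEs (item 6). If the definition leaves out a reaction that the protocol itself foresees, a low AE count may partly reflect the wording rather than what participants experienced.

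**Working it through.** No sample size, power or event-rate figure bears on this point, so the check is textual. The definition has four conditions: the event is (U) unexpected, (D) undesirable, (T) physical or psychological, and (C) possibly caused by participation. As written, all four must hold, and they apply to serious and non-serious events alike.

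1. **Against the attribution classes.** *Not related* says the event clearly belongs to the participant's clinical state, so it fails C. *Remote* says this is only most likely, which leaves a causal link possible, so C can hold. *Possible* and *Probable* satisfy C. Result: 1 of 4 classes is logically excluded.

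2. **Against the severity scale.** Grade 1 treats mild discomfort as a gradable AE. Section 11.1 names discomfort as a foreseen risk. If U means not foreseen in the protocol, the most obvious Grade 1 event in this study fails U.

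3. **Against item 5.** It separates SAEs that are at least possibly related from all others and confirms reporting of both. Under C, an SAE with no possible causal link is not an AE, so at least part of the second group should not exist.

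4. **Against the two named main risks.**
   - Distress from the questions meets D, T and C. Whether it meets U depends on a word the plan does not define. Read literally, it can be left out.
   - A breach of confidentiality is not itself a physical or psychological occurrence, so it fails T. Psychological harm that follows a breach could meet T. Neither item 2 nor the list of DSMB report contents names breaches.

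5. **From intake to count.** Intake is wider than the definition: staff pass on any concerns (item 2) and safety concerns raised by participants (item 1). But item 1 trains staff to identify adverse events as defined in the plan, and the DSMB summary and annual report count AEs. A concern that fails the definition can reach the investigators, but no rule puts it into those counts.

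6. **The SAE tag.** The scale ties seriousness to Grade 4, while item 2 says a separate SAE definition is used. The plan does not say how the two relate.

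**The case against.** The strongest reply is that little is lost in practice. Any concern goes to the investigators, who judge causality; nothing tells staff to hold back a report; and the only explicit rule against recording concerns unchanged pre-existing conditions. This stands against any claim that events are screened out before they are reported or recorded. It does not answer step 5, because the counts are still counts of AEs.

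A second reply is that unexpected may mean unlikely rather than unforeseen. Section 11.1 says no earlier participant reported significant distress from similar questions, item 2 calls adverse reactions highly unlikely, and Grade 1 points to discomfort being counted. This is a fair reading, and it means that exclusion of distress is not established, only allowed. The wording should not leave the choice open.

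A third reply is that the item 5 sentence is the funder's template prompt, and that the sponsor's own 48-hour commitment carries no relatedness limit. Both are true. But the sponsor answered yes to the prompt, and a commitment without a relatedness limit also sits outside a definition that has one.

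A reader might also infer that a student hospitalized at Grade 3 would miss the 48-hour route, or that death is not covered. The documents do not support this. The trigger is a serious event, site designees separate SAEs from AEs, and the SAE definition they would use is not reproduced.

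**Conclusion.** The concern holds as an internal conflict in the DSMP that creates a risk of undercounting AEs. Its size is one of four attribution classes excluded by the definition, one of the two named main risks (distress) excludable on a literal reading, and the other (breach) outside by type. This rests on taking item 2's written definition as the operative one and, for distress, on reading unexpected as not foreseen in section 11.1. Agreement with the FDA text cannot be checked from the documents and plays no part here.

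Some stronger conclusions are tempting but not supported. A reader might infer that two attribution classes are empty, but *Remote* is compatible with a possible causal link. A reader might infer that AE counts would be near zero whatever happens, but the wider intake and the Grade 1 wording make that unproven, and no undercount can be calculated. A reader might infer that a comparison of AEs between arms would be spoiled, but the plan specifies no such comparison. In a study described as minimal risk this is a matter of wording, but it should be corrected because the DSMB relies on the counts.

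**What to change.** Amend DSMP item 2 as follows.

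- Delete the word unexpected and the causal clause from the AE definition. Count as an AE any undesirable physical or psychological occurrence that staff observe, or that a participant reports to staff, from consent to the 6-month follow-up.
- Keep the exclusion of unchanged pre-existing conditions.
- State that consequences endorsed on the outcome surveys are outcomes, not AEs. Without this line a broad definition could sweep in the YAACQ. It has 48 yes/no items, and section 9.2 repeats the baseline measures at 1, 3 and 6 months, so 48 × 3 = 144 responses per participant, in students selected for at least two recent consequences. The surveys are also not monitored individually (items 1 and 10).
- Have the investigators then judge expectedness, and relatedness on the existing four-class scale.
- List confidentiality breaches as a reportable event in the DSMB report (item 1.D).
- Reconcile the SAE tag on Grade 4 with the SAE definition the plan invokes, and quote that definition.

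The cost is a DSMP wording change and a short retraining note for staff. No intervention, sample size or efficacy analysis changes. The downside is likely to be a few more logged events and a slightly less favourable AE count; the documents give no basis for a number.
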